18. RECORDS RETENTION

All study-related correspondence, subject records, consent forms, Authorization for Use/Disclosure of Health Information Forms or similar medical treatment privacy law documentation, records of the distribution and use of all study products, and original case report forms should be maintained by the investigator.

The investigator must maintain and have access to the following essential documents until notified by the Sponsor. Note: This may be for a minimum of 15 years after completion of the study. AMO requires notification if the investigator wishes to relinquish ownership of the data so that mutually agreed-upon arrangements can be made for transfer of ownership to a suitably qualified, responsible person.

- All case report forms
- All adverse event information (i.e., medical records, medical reports and/or judgments from colleagues or outside specialists who assisted in the treatment and follow-up of the subject)
- Investigational supply records/inventory
- IRB approval documentation
- Study correspondence
- Study agreements
- Site visit documentation
- Protocol(s)
- Subject log(s)
- Clinical Investigator's Brochure
- Completed subject informed consent forms and medical privacy forms (e.g., Authorization for Use/Disclosure of Health information)
- Subject medical chart/clinic notes (Not applicable for transfer of ownership to AMO)

19. TERMINATION OF THE INVESTIGATION

The clinical investigation will be suspended in the event of high levels of complications and/or adverse events that are unexpected in nature and/or severity and evaluated as to causality relative to the study device. The clinical investigation may be suspended if the Medical Monitor or the IRB, upon review and evaluation of the clinical data, finds unacceptable clinical performance or the level of single or total complications and/or adverse events unacceptable for continuation of the investigation.

If causality is shown not to be related to the study device, the study may be resumed in accordance with the IRB and regulations of the FDA. The study will be terminated if causality is shown to be related to the study device.

Additionally, the investigator or AMO may stop a subject's participation at any time. AMO may also stop the study at any time for reasons it determines appropriate. However, no suspension of the study would be made to disadvantage the study subjects. Following suspension of the study for any reason, all study subjects who have already received treatment would continue to be followed through completion of the study visit schedule.

20. STATISTICAL METHODS

This section highlights the analyses to be performed for key study endpoints. The key study timeframe for effectiveness endpoints will be 1 month and for safety endpoints the key study timeframe will be 6 months, although data will be reviewed at other time points

as well. TECNIS Models ZHR00 and ZQR00 will both be compared to TECNIS Symphony control separately and independently for all analyses. All data will be reported by IOL group.

20.1 ANALYSIS POPULATION

The safety population (SP) of all subjects implanted who have available data will be used for all analysis. No data imputation will be performed for missing data. For the monocular endpoints, the safety population will consist of first eyes implanted with a study IOL; for binocular endpoints, the safety population will consist of subjects implanted with the same IOL in both eyes. The primary analysis population will be the safety population (SP) for all endpoints.

20.2 PRIMARY STUDY ENDPOINTS

Primary Effectiveness Endpoints

MODEL ZHR00: MONOCULAR DISTANCE CORRECTED NEAR VISUAL ACUITY (DCNVA) AT 40 CM

The primary effectiveness endpoint for the Model ZHR00 IOL is mean (LogMAR), photopic, monocular, first-eye, distance corrected near visual acuity (40 cm) at 1 month postoperative. Note that a lower LogMAR value is a better acuity and a higher LogMAR value is a poorer acuity. The mean, SD, median, minimum, maximum and 95% confidence interval (CI) will be reported by IOL group.

- A statistical comparison between the Model ZHR00 and control lens groups will be performed using a 1-sided, 2-sample, t-test with an alpha set at 0.025. The null hypothesis is that the mean monocular DCNVA for the Model ZHR00 eyes is worse than or equal to that for control eyes. The alternate hypothesis is that the mean monocular DCNVA for Model ZHR00 eyes is better than that for control eyes.

$H_0: \mu_c - \mu_t \leq 0$ (Model ZHR00 lens is worse than (higher LogMAR) or equal to control)

$H_1: \mu_c - \mu_t > 0$ (Model ZHR00 lens is better (lower LogMAR) than control)

where

μ_t = mean LogMAR DCNVA for the Model ZHR00 lens

μ_c = mean LogMAR DCNVA for control lens

Reject the null hypothesis if one-sided p-value ≤ 0.025 .

The success criterion is a statistically significantly lower mean LogMAR value for the Model ZHR00 investigational lens compared to the control lens ($p \leq 0.025$).

MODEL ZQR00: MONOCULAR DISTANCE CORRECTED NEAR VISUAL ACUITY (DCNVA) AT 40 CM

The primary effectiveness endpoint for the Model ZQR00 IOL is mean (LogMAR), photopic, monocular, first-eye, distance corrected near visual acuity (40 cm) at 1 month postoperative. Note that a lower LogMAR value is a better acuity and a higher LogMAR value is a poorer acuity. The mean, SD, median, minimum, maximum and 95% CI will be reported by IOL group.

- Analysis for the Model ZQR00 will be similar to the Model ZHR00 analysis described above. A statistical comparison between the Model ZQR00 and control lens groups will be performed using a 1-sided, 2-sample, t-test with an alpha set at 0.025. The null hypothesis is that the mean monocular DCNVA for the Model ZQR00 lens eyes is worse than or equal to that for control eyes. The alternate hypothesis is that the mean monocular DCNVA for Model ZQR00 eyes is better than that for control eyes.

$H_0: \mu_c - \mu_t \leq 0$ (Model ZQR00 lens is worse than (higher LogMAR) or equal to control)

$H_1: \mu_c - \mu_t > 0$ (Model ZQR00 lens is better (lower LogMAR) than control)

where

μ_t = mean LogMAR DCNVA for the Model ZQR00 lens

μ_c = mean LogMAR DCNVA for control lens

Reject the null hypothesis if one-sided p-value ≤ 0.025 .

The success criterion is a statistically significantly lower mean LogMAR value for the Model ZQR00 compared to the control lens ($p \leq 0.025$).

Primary Safety Endpoints

MODEL ZHR00: RATES OF ADVERSE EVENTS VS. ISO SPE RATES

The primary Model ZHR00 safety endpoint for this study is the rate of adverse events vs. ISO SPE rates at 6 months postoperative. The frequency and proportion of first eyes, second eyes, and all subjects with these events will be reported over time by IOL group. Statistical comparisons to ISO SPE rates will be based on first-eye data; adverse event rates for the Model ZHR00 investigational lens first eyes will be compared to the ISO SPE rates using a one-sided, exact test based on the binomial distribution. The null hypothesis is that the AE rate for the Model ZHR00 investigational lens eyes is lower than or equal to the ISO SPE values, and the alternative hypothesis is that the AE rate for study eyes is higher than the ISO SPE values.

$H_0: p_t \leq p_i$

$H_1: p_t > p_i$

where

p_t = proportion of Model ZHR00 investigational lens eyes with the AE

p_i = proportion of eyes reported in ISO SPE rates with the AE

Reject the null hypothesis if one-sided p-value < 0.05.

MODEL ZQR00: RATES OF ADVERSE EVENTS VS. ISO SPE RATES

The primary Model ZQR00 safety endpoint for this study is the rate of adverse events vs. ISO SPE rates at 6 months postoperative. The frequency and proportion of first eyes, second eyes, and all subjects with these events will be reported over time by IOL group. Statistical comparisons to ISO SPE rates will be based on first-eye data; adverse event rates for Model ZQR00 investigational lens first eyes will be compared to the ISO SPE rates using a one-sided, exact test based on the binomial distribution. The null hypothesis is that the AE rate for Model ZQR00 investigational lens eyes is lower than or equal to the ISO SPE values, and the alternative hypothesis is that the AE rate for study eyes is higher than the ISO SPE values.

$$H_0: p_t \leq p_i$$

$$H_1: p_t > p_i$$

where

p_t = proportion of Model ZQR00 investigational lens eyes with the AE

p_i = proportion of eyes reported in ISO SPE rates with the AE

Reject the null hypothesis if one-sided p-value < 0.05.

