10.4 RANDOMIZATION AND MASKING

A randomization list will be created by the AMO biostatistician for each investigative site and the randomization code will be uploaded into the electronic data capture system (EDC). Subjects will be randomized to the investigational Model ZHR00 IOL, the investigational Model ZQR00 IOL or the Symphony control IOL. Unmasked study personnel at the site will be trained to the randomization process through the EDC system and will randomize subjects after the subject has signed the informed consent form, has met all eligibility criteria and the investigator has documented which eye will be the first implanted.

As part of the informed consent process, the investigator or delegate will explain to the subject the requirements of a randomized study and the differences expected between the three lens models: the Models ZHR00 and ZQR00 investigational lenses and the Symphony control lens. The surgeon and the operative staff will know which lens type is implanted. There may also be site coordinators and other site study staff, such as those performing slit-lamp exams, who will be unmasked. Unmasked study site staff will be instructed not to disclose the lens type the subject received or to talk about the lens to any masked evaluators or to the study subjects.

The subjects and the study technicians performing the postoperative vision tests are to be masked through study completion. To maintain subject/technician-masking through the 6-month study exams, a masking plan will be tailored for each site to detail how lens assignment information will be concealed from masked technicians. Recommended steps to maintain masking include ensuring that all items pertaining to lens group assignment and lens implantation records are kept separately from all other study documents and subject medical records until after completion of the final study visit. For example, lens stickers (indicating the lens model implanted) may be kept in the operating room study notebook until completion of the final study visit, at which time they may be placed in the subject medical charts. In the meantime, temporary lens stickers (without lens model designations) may be used in the subject's medical chart.

To maintain subject masking, a temporary IOL implant identification card will be issued to the subject at the time of surgery. Following completion of the final study exam, each subject will be given the permanent IOL implant identification card.

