2 ANALYSIS POPULATIONS

2.1 ANALYSIS POPULATIONS

The analysis population will be the safety population, which includes all eyes implanted with either a test or control IOL(s) and with data available at the time of analysis (i.e., no data imputation). For bilateral testing and subject-based questionnaire, only subjects binocularly implanted with the same test lens or the same control lens will be included. If an eye or a subject are discontinued during the study, any available data prior to the study exit will be presented.

Version 1.0 1 SAP/EROV-121-NGPC

The primary analysis will be based on first-eye or binocular outcomes (as appropriate per effectiveness endpoints), unless stated otherwise. However, select data such as medical/lens complications and adverse events will also be reported separately for second eyes. Binocular data will be reported for those who are implanted with the same IOL (test or control) in both eyes.

The two test lens, TECNIS Model ZHR00 and Model ZQR00 IOLs, will be compared to the TECNIS Symfony control IOL separately and independently. All endpoint comparison analysis to the control lens will present in two separate tables as follows:

- ZHR00 vs. control
- ZQR00 vs. control

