2.4 RANDOMIZATION

Subjects are to be implanted with the same IOL in both eyes, the ZHR00 IOL, the ZQR00 IOL or the Symfony control IOL, according to a randomization schedule. AMO will use a centralized electronic randomization system (Merge eClinical OS).

If a surgeon implants the wrong study lens, i.e., other than the one on the randomization schedule, the subject's study data will be analyzed according to the actual lens received; however, the number of these events will be reported.

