3.2 DEMOGRAPHICS

Subject demographic data including age, sex, race, and eye color will be presented by IOL group. Age will be determined at the time of the preoperative visit and will be categorized by less than 60, 60 to 69, 70 to 79, and equal to or older than 80 years old. In addition, age will be summarized with descriptive statistics. The frequency distributions of sex, race, and iris color will also be tabulated.

Comparisons between IOL groups will be performed using Fisher's exact test for demographic categorical data. The null hypothesis is that there is no difference in the proportion with specific responses between IOL groups, whereas the alternative hypothesis is that there is a difference in at least one proportion between IOL groups. For comparisons between IOL groups for mean age, the two-sample t-test will be used. The null hypothesis is that there is no difference in mean values between IOL groups, whereas the alternative hypothesis is that there is a difference in mean values between IOL groups. Two-sided testing with an alpha level of 0.05 will be used for all demographic variables.

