5 POSTOPERATIVE ANALYSES – PRIMARY EFFECTIVENESS ENDPOINTS

5.1 MODEL ZHR00: MONOCULAR DISTANCE CORRECTED NEAR VISUAL ACUITY (DCNVA) AT 40 CM

The primary effectiveness endpoint for the Model ZHR00 IOL is mean (LogMAR), first-eye, monocular, photopic, distance corrected near visual acuity (40 cm) at 1 month postoperative. The mean, SD, median, minimum, maximum and 95% C.I. will be reported by IOL group. Results will be reported by lens group for first eyes using one-sided, two-sample t-tests with alpha level of 0.025. Note that a lower LogMAR value is a better acuity and a higher LogMAR value is a poorer acuity. The null hypothesis is that the mean monocular DCNVA for the Model ZHR00 eyes is worse than or equal to that for control eyes. The alternate hypothesis is that the mean monocular DCNVA for Model ZHR00 eyes is better than that for control eyes.

```
H_o: \mu_c - \mu_t \le 0 (ZHR00 is worse than (higher LogMAR) or equal to control) H_1: \mu_c - \mu_t > 0 (ZHR00 is better (lower LogMAR) than control) where \mu_t = \text{mean LogMAR DCNVA} for Model ZHR00 lens \mu_c = \text{mean LogMAR DCNVA} for control lens Reject the null hypothesis if one-sided p-value \le 0.025.
```

The success criterion is a statistically significantly lower mean LogMAR DCNVA score for the Model ZHR00 investigational lens compared to the control lens ($p \le 0.025$).

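### SAP 2.4 classifies wrong-lens subjects by lens received for every endpoint, so the randomized superiority test on DCNVA has no analysis by randomized group; adjusting that test for age is an optional efficiency gain

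*Protocol*

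**What the plan says.** **Primary test.** Protocol 20.2 compares each investigational lens with control on mean 1-month first-eye LogMAR DCNVA. The comparison "will be performed using a 1-sided, 2-sample, t-test with an alpha set at 0.025". SAP 5.1 and 5.2 agree: "Results will be reported by lens group for first eyes using one-sided, two-sample t-tests with alpha level of 0.025". No site term or covariate is named.

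**Wrong study lens.** Under SAP 2.4, if the implanted study lens is not the one on the randomization schedule, "the subject's study data will be analyzed according to the actual lens received". The number of such events is to be reported. The rule covers all endpoints.

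**Population.** SAP 2.1 has a single analysis population, "which includes all eyes implanted with either a test or control IOL(s) and with data available at the time of analysis". Protocol 20.1 makes the same safety population primary for all endpoints and adds: "No data imputation will be performed for missing data".

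**Randomization and age.** Protocol 10.4 states: "A randomization list will be created by the AMO biostatistician for each investigative site". Neither that section nor SAP 2.4 says whether the lists are blocked. SAP 3.2 states: "Age will be determined at the time of the preoperative visit". Age then appears only in the demographic comparison.

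**The concern.** Success on the primary endpoint is a claim of superiority from a randomized comparison. Randomization supports that claim only if subjects stay in the group to which they were assigned. SAP 2.4 instead lets an event after randomization, the lens actually implanted, decide the group. That is natural for safety rates, which concern the device in the eye, but here it also governs the superiority p-value, and no second analysis shows whether the answer depends on it. Surgeons and operative staff know the lens (Protocol 10.4) and sites hold all three models on consignment (Protocol 7.1), so an error that is not purely random cannot be excluded.

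A smaller matter is efficiency. The lists are made by site and age is recorded at baseline, but the primary test uses neither. At stake is some power for differences below 1 line, in a study that Protocol 4 describes as a step towards choosing a final design.

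**Working it through.** **Inputs from the documents** (Protocol 20.6, SAP 8): SD 1.6 lines, 65 per group, one-sided alpha 0.025, difference 1 line, stated power 90%.

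**Assumed, because the documents do not give them:** k = 1, 2 or 3 wrong-lens subjects, all randomized to test and given control; their prognosis d = 0.5 SD = 0.8 line worse or better than average; share of variance explained by age (R²) 0, 5 or 10%; site intraclass correlation (ICC) 0 to 0.20; block size.

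**1. The plan's own power.** SE = 1.6 × √(2/65) = 0.2807 line. Noncentrality = 1/0.2807 = 3.563. With 128 df the critical value is 1.979 and power is 94.3%. The stated 90% is therefore not reproduced, but the difference is on the safe side: 55 per group would give 90.1%.

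**2. Analysis by lens received, no true difference.** Moving k subjects from test to control raises the control mean by kd/(65+k) and lowers the mean of those left in test by kd/(65−k). The apparent benefit is the sum. It is tested with SE = 1.6 × √(1/(65−k) + 1/(65+k)), about 0.281.

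| k | Shift (lines) | Type I, 0.5 SD worse | Type I, 0.5 SD better |
|---|---|---|---|
| 1 | ±0.025 | 0.031 | 0.020 |
| 2 | ±0.049 | 0.037 | 0.016 |
| 3 | ±0.074 | 0.045 | 0.013 |

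For example, with k = 2: 1.6/67 + 1.6/63 = 0.049. A simulation of the worse-reading case (300,000 trials per k) gave 0.030, 0.036 and 0.043. The last column also describes worse-reading subjects who move from control to test. Errors in both directions partly cancel. If d = 0 there is no shift.

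**3. Analysis by randomized group.** Type I error stays at 0.025. A true 1-line effect is diluted to 1 − k/65, about 1.5% per case: 0.985, 0.969 and 0.954 line for k = 1, 2, 3. Dividing by 0.2807 gives power of 93.6, 92.9 and 92.1%.

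**4. Age in the model.** SD = 1.6 × √(1 − R²), 127 df, variance inflated by 1 + 1/126 for chance imbalance in age.

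| R² | Power, 1 line | Power, 0.75 line (assumed effect) |
|---|---|---|
| Unadjusted | 94.3% | 75.6% |
| 0 | 94.1% | 75.2% |
| 5% | 95.1% | 77.3% |
| 10% | 96.0% | 79.5% |

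At 1 line the change is −0.2, +0.8 and +1.8 points.

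**5. Site in the model.** Simulation with 220 randomized to three arms over 14 sites, 11% random dropout and 20,000 trials per cell (Monte Carlo SE about 0.16 points). Change in 1-line power from adding site:

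| Lists | ICC 0 | 0.05 | 0.10 | 0.20 |
|---|---|---|---|---|
| Blocks of 3 | −0.4 | +0.2 | +0.8 | +1.6 |
| Blocks of 6 | −0.5 | +0.1 | +0.9 | +1.6 |
| Unblocked | −2.6 | −1.4 | −0.2 | +1.6 |

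With blocks of 3, the unadjusted t-test has type I error 0.0253, 0.0236, 0.0194 and 0.0145 across these ICCs. Within simulation error it is at or below 0.025.

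**The case against.** The strongest case on the other side has four parts.

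- **No prognosis-driven swap is described.** Under Protocol 10.6, a complication that prevents use of the study lens leads to a non-investigational back-up lens, and a subject to whom this happens in the first eye is exited. That route does not move anyone between study arms, and SAP 2.4 concerns only a wrong study lens. This stands, and it limits the likely number of cases. It does not rule out other errors by unmasked staff, for which SAP 2.4 itself makes provision.
- **The bias need not favour the test lens.** This also stands. The two type I columns are mirror images, and the documents give no reason to prefer either.
- **The unadjusted t-test is valid, prespecified and has more power than stated.** This stands in full, which is why adjustment is only an option.
- **Age is an arbitrary covariate.** Nothing in the documents links age to DCNVA, whereas the defocus curves are stratified by pupil size (Protocol 10.7, SAP 7.3). This stands in part. Protocol 10.3 lists a preoperative photopic pupil measurement, but the pupil-size row of Appendix A is marked only at 1 and 6 months. With no imputation, missing values would drop subjects. Age has no such gap.

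A reader might infer that a single safety population means no subject is compared as randomized. The documents do not support that: for everyone who receives the assigned lens, lens received and lens randomized are the same. Nor do they support the inference that ignoring site invalidates the test or inflates its type I error. If the lists are blocked and sites differ, the test is conservative. If they are unblocked, its standard error is correct.

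**Conclusion.** The point about lens received holds, as a matter for consideration and not as a demonstrated bias. The superiority test lacks an analysis by randomized group, and the effect depends on how many wrong-lens cases occur and whether they are related to prognosis. The documents give neither. If the errors are unrelated, nothing is lost. Under an assumed 0.5 SD relation and 1 to 3 cases, all from test to control, type I error lies between 0.013 and 0.045 against a nominal 0.025. That the number will be small is a judgement. The protection costs so little that the size of the risk need not be settled first.

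The covariate point is an optional efficiency gain and not an error. Its size rests on an assumed R² for age. For site, even the sign depends on blocking and on ICC.

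**What to change.** **Main change, SAP 2.4.** For the primary superiority test only, analyse wrong-lens subjects who have 1-month data in their randomized group. Keep lens received for safety endpoints and as a sensitivity analysis of the primary endpoint. The safety population is unchanged and no new data are needed. The cost is the dilution shown in step 3.

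**Optional change, Protocol 20.2 and SAP 5.1 and 5.2.** Replace the primary test with a linear model of 1-month first-eye LogMAR DCNVA on lens group and preoperative age, one-sided at 0.025, and keep the t-test as a sensitivity analysis. This uses one degree of freedom. Because it alters the protocol, it also needs the approvals in Protocol 12. A lighter alternative is to keep the t-test as primary and add the age model as supportive.

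**Site.** State whether the site lists are blocked. Add a site term only if they are, with a rule for pooling sites that lack a subject in either compared group. It costs up to 13 degrees of freedom and, if sites do not differ, up to about 0.5 points of 1-line power.

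Settle these choices before outcome data are seen.
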